7.3 Handling of Dropouts and Missing Data

Missing data mechanisms will be explored, and sensitivity analyses will be conducted on primary outcomes to assess the robustness of the described analyses. Methods employed for sensitivity analyses may include multiple imputation or inverse probability weighting methodology. Imputation is not planned for secondary analyses. For further details on sensitivity analyses involving missing data see Attachment 16.2.

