9 EFFICACY ANALYSES

9.1 Overview of Efficacy Analyses Methods

- All efficacy analyses will be performed on the ITT population.
- All efficacy variables will be summarized by treatment group at baseline and at the 3, 6, and 12-month time points. N, mean, standard deviation, minimum, and maximum will summarize continuous efficacy variables, whereas number and percent will summarize categorical efficacy variables.
- Unless otherwise noted, all analyses of dichotomous outcomes, measured at respective endpoints, will be performed using a generalized linear mixed model. Models will be adjusted for stratification by clinical site and UUI severity group. If there are not enough patients in every clinical site to include the variable in the models as a fixed effect,

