OAB-SAT-q Convenience Score at 12 Months	Continuous	
The OAB-SAT-q Convenience Score will be computed at 12 months (and 3 and 6 months) using the standard scoring algorithm. Specifically, instructions are to use the response to question 4 (1=Extremely Inconvenient, ..., 6=Extremely Convenient), then subtract from the maximum possible sum score (6) and divide by the range of possible scores (6-1=5), then multiply by 100. If the response to question 4 is missing then no score is calculated. If data for an assessment time point are missing, the outcome variable will be coded as missing.

OAB-SAT-q Preference Indicator at 12 Months	Dichotomous	
The OAB-SAT-q Preference Score will be computed at 12 months (and 3 and 6 months) using the standard scoring algorithm. Specifically, the indicator is set to 1 if the response to question 8 is either “Slight preference for the treatment I am receiving now” or “Definitely prefer the treatment I am receiving now”, otherwise it is set to 0. If the response to question 8 is missing then indicator is calculated. If data for an assessment time point are missing, the outcome variable will be coded as missing.
 
The score is calculated as the percentage of participants with Indicator=1 among all non-missing Indicators.

Network

Protocol ESTEEM Statistical Analysis Plan

Variable	Type	Definition
Retreatment at 12 months	Categorical and Dichotomous	
The types of retreatment for SUI or UUI will be identified and categorized from the Additional Therapy and Concomitant Medications forms. Further details can be found in Attachment 16.1.
 
An indicator of retreatment will be calculated for each subject where subjects with retreatment identified above will be assigned “Yes”, otherwise subjects are assigned “No”. The rate of retreatment is calculated as the percentage of participants with indicator=“Yes” among all non-missing indicators.

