Time-to-Failure	Semi-continuous number of days/years until failure	
Failure = The first time at which a subject seeks any additional treatment for SUI or UUI/OAB symptoms as determined by the Additional Therapy and Concomitant Medications forms. Further details can be found in Attachment 16.1.
 
Success = Any subject for whom no additional treatment for SUI or UUI/OAB symptoms is identified, censored at 12 months if the subject completed the entire follow-up period. Subjects lost to follow-up will be censored at the time of their last visit (scheduled or unscheduled).

Sling Revision for Worsened OAB Symptoms at 12 months	Dichotomous	
An indicator of sling revision will be calculated for each subject where those who have a sling revision for worsening OAB listed on the Additional Therapy form will be assigned a “Yes”, otherwise subjects are assigned “No”.
 
The rate of sling revision is calculated as the percentage of participants with indicator equal to “Yes” among all non-missing indicators.

Change from Baseline IIQ Physical Activity Score at 12 Months	Continuous	
The Incontinence Impact Questionnaire-Physical Activity Score will be computed at baseline and 12 months (and 3 and 6 months) using the standard scoring algorithm. Specifically, instructions are to average responses across questions A, B, C, D, E, and U (0=Not at all, 1=Slightly, 2=Moderately, 3=Greatly), and then multiply by 100/3. If any responses are missing, then the score will be calculated as the average of the non-missing responses. The outcome will then be computed as the difference in score at 12 months

Network

Protocol ESTEEM Statistical Analysis Plan

Variable	Type	Definition
		(and 3 and 6 months) and the score at baseline. If data for an assessment time point are missing, the outcome variable will be coded as missing.

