16 ATTACHMENTS

16.1 Defining Treatment Failures and Retreatment Rates

Treatment failure is defined as initiation of any additional treatment for either SUI or UUI/OAB symptoms. These will be determined through an analysis of the Additional Therapy Form (CRF #31) and Concomitant Medications Form (CRF #28).

- a. Additional Therapy Form – Any subject with a reported reason for visit of 2, 3, 4, 5, 10, 11, 12, 13, 14, 15, or 17 will be considered to have treatment failure at the time of the reported treatment. Similarly, each subject will be considered to have had retreatment.

2. Reason for Visit	6 = Pain	10 = Botox	16 = Other, specify
1 = UTI	7 = Infection	11 = Posterior tibial nerve stimulation symptoms	17 = sling removal
2 = Behavior Therapy	8 = Decrease efficacy (worsening incontinence)	12 = sling revision	18 = UUI/OAB
3 = PF Therapy	9 = Retention of urine or incomplete bladder emptying	13 = sling placement	19 = SUI symptoms
4 = Anticholinergic medication		14 = sacral neuromodulation	
5 = Pelvic PT		15 = Continence pessary	

- b. Concomitant Medications – Any subject with medications or therapies that are known treatments of OAB, UUI, or SUI (Detrol, Ditropan, Vesicare, Hyoscyamine, Oxybutynin) or for whom UUI/OAB, SUI Therapy, or Voiding Dysfunction indicators are marked will be considered to have treatment failure at the start date of the medication if it is after randomization. Similarly, each subject will be considered to have had retreatment.

Medication Name	Start Date (DD/MMM/YYYY)	Stop Date (DD/MMM/YYYY)	PRN	UUI/OAB Therapy	SUI Therapy	Voiding dysfunction	Continuing at End of Study
	___/___/___	___/___/___					

In general, any adverse events that could be considered treatment failures will be requested to be removed and re-entered on the additional therapies form if applicable.

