16.2 Missing Data and Multiple Imputation

Sensitivity analysis to see the impact of missing data on the primary outcome (UDI Total score) and the dryness and MID indicators will be performed using multiple imputation. Missing data at 3, 6, and 12 months will be imputed using non-missing data from prior time points (including baseline) to inform the imputed values as well as age, treatment, race, ethnicity, BMI, smoking status, estrogen use (oral/patch), site, incontinence episode group (from randomization), vaginal delivery count, and private insurance indicator. Missingness will first be assured to monotone missing (i.e. ensure not missing prior time points when later time points are present) 25 times using MCMC methods, then all other missing data will be imputed for each of the 25 monotone-missing datasets using regression and logistic imputation methods. Each imputed dataset will be fit using the models described in Section 9.3. Differences between groups for each imputed dataset will then be combined to estimate average effects and standard errors and compared to the model without imputation. All imputation will be performed using SAS v9.4.

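### SAP 9.2 counts women lost before 12 months as 'No' for retreatment, so the crude rate can read slightly low; report the planned Kaplan-Meier estimate beside it

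*SAP*

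**What the plan says.** In SAP 9.2, the row for retreatment at 12 months states that "subjects with retreatment identified above will be assigned “Yes”, otherwise subjects are assigned “No". The next sentence begins "The rate of retreatment is calculated as the percentage of participants with" and divides the 'Yes' women by all women with a non-missing indicator. Neither that row nor Attachment 16.1 says when an indicator is missing. The voiding-frequency and dryness rows in the same table do carry such a rule. The sling-revision row has the same structure: women with a revision "listed on the Additional Therapy form will be assigned a “Yes”, otherwise subjects are assigned “No".

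Time-to-Failure, in the same table, handles loss differently: "Subjects lost to follow-up will be censored at the time of their last visit (scheduled or unscheduled". Attachment 16.1 defines failure and retreatment from the same two forms and dates the event; for the Additional Therapy form the woman "will be considered to have treatment failure at the time of the reported treatment". SAP 13 replaces the planned survival model with Kaplan-Meier, because relatively few women met the failure criteria.

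Exploratory aim 5 (SAP 3.1.3) compares the proportions starting additional treatment, and SAP 9.5.5 describes the rates. SAP 9.1 gives a default for yes/no outcomes: "Unless otherwise noted, all analyses of dichotomous outcomes, measured at respective endpoints, will be performed using a generalized linear mixed model". The missing-data work in Attachment 16.2 is a "Sensitivity analysis to see the impact of missing data on the primary outcome (UDI Total score) and the dryness and MID indicators"; retreatment is not on that list. SAP 7.3 adds: "Imputation is not planned for secondary analyses".

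**The concern.** A 'No' at 12 months should mean that the woman was followed for 12 months without retreatment. As coded, it also covers women whose later months were never observed. SAP 5.1 keeps in the analysis any eligible randomized woman with outcome data at any point from 3 to 12 months. Protocol 3.4.1.c asks that additional treatment wait until 3 months after surgery. A woman last seen at 3 months therefore has nearly all of her planned at-risk time unobserved, yet enters the denominator as event-free.

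The SAP would then produce two 12-month retreatment figures from the same events, treating the same lost women in two ways, and 9.2 gives the name of retreatment rate to the uncensored one. At stake are the level of each arm's rate and, if loss differs by arm, the between-arm difference for aim 5.

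**Working it through.** **Inputs from the documents.** Additional treatment 30% (sling only) and 20% (sling plus behavioral therapy): SAP 6. Dropout 15% on 200 per group, 472 in total: SAP 6.3. Check: 200 / 0.85 = 235.3, rounded up to 236 per arm, and 2 × 236 = 472, as stated.

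**Assumptions.** Events and losses are uniform over 3 to 12 months, and lost and retained women have the same event rate. Half of lost women's events then precede loss (r = 0.5). Because SAP 13 reports few failures, 10% versus 5% is added as an assumed alternative.

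**Crude rate.** With true rate p, share lost d, and share r of lost women's events recorded:

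coded rate = p × [1 − d × (1 − r)]

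| Case | Factor | True 30% / 20% | True 10% / 5% |
|---|---|---|---|
| d = 0.15, r = 0.5 | 0.925 | 27.75% / 18.5% | 9.25% / 4.63% |
| d = 0.15, r = 0.8 | 0.970 | 29.1% / 19.4% | 9.7% / 4.85% |
| d = 0.081, r = 0.5 | 0.9595 | 28.8% / 19.2% | 9.6% / 4.8% |
| d = 0.15, r = 0 (all lost at 3 months) | 0.850 | 25.5% / 17.0% | 8.5% / 4.25% |

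The third row assumes that half of the losses give no data from 3 to 12 months and leave the analysis under SAP 5.1: 0.075 / 0.925 = 0.081.

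**Difference and ratio, first row.** 27.75 − 18.5 = 9.25 points, 0.75 below the true 10. 9.25 − 4.625 = 4.625 points, about 0.4 below the true 5. The ratios stay at 1.5 and 2.0. In simulation with 236 per arm, the 95% confidence interval half-widths for the Kaplan-Meier difference are about 8.1 and 4.9 points.

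**Unequal loss (assumed), r = 0.5.**
- 20% lost in the control arm, 10% in the other: 0.30 × 0.90 − 0.20 × 0.95 = 8.0 points; for 10/5, 0.10 × 0.90 − 0.05 × 0.95 = 4.25 points.
- Reversed: 0.30 × 0.95 − 0.20 × 0.90 = 10.5 points; for 10/5, 0.10 × 0.95 − 0.05 × 0.90 = 5.0 points.

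**Kaplan-Meier under the same assumptions.** Simulated 12-month estimates average about 30% / 20% and 10% / 5%, so the censored analysis removes the bias when loss is unrelated to retreatment.

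**Where Kaplan-Meier goes wrong.**
- *Late-found events.* Suppose 60% of post-loss events are found later, so r = 0.5 + 0.5 × 0.6 = 0.8. If they are kept while event-free lost women are censored at their last visit, Kaplan-Meier reads about 31.2% / 20.8%; crude is 29.1% / 19.4%. Counting only events up to the censoring date brings it back to about 30% / 20%.
- *Lost women have half the event rate, overall rates held.* Crude = p × (0.85 + 0.15 × 0.5 × 0.5) / (0.85 + 0.15 × 0.5) = p × 0.8875 / 0.925 = 28.8% / 19.2%. Kaplan-Meier (simulated) is about 31.3% / 20.8%, about as far above the truth as crude is below.
- *Lost women have twice the rate.* Kaplan-Meier is about 28% / 19%, crude about 26% / 17%.

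**A tempting repair that fails.** Setting only event-free losses to missing gives 0.2775 / (0.2775 + 0.85 × 0.70) = 31.8% and 0.185 / (0.185 + 0.85 × 0.80) = 21.4%, which is too high.

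**Sling revision.** At 1%, the top of the 0 to 1% that Protocol 5.1.c cites (there for retention), 236 × 0.01 = 2.36 events per arm. Missed: 2.36 × 0.15 × 0.5 = 0.18, or 2.36 × 0.15 = 0.35 if none are recorded after 3 months.

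**The case against.** Five replies have weight.

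1. **Events may be captured after loss.** SAP 10.2 finds reoperations, including those for recurrent symptoms, by chart review and physician report. Attachment 16.1 asks that adverse events amounting to treatment failure be re-entered on the additional therapy form. This stands: the bias shrinks as capture improves and vanishes if capture is complete. It also means that a careless Kaplan-Meier estimate can overshoot.
2. **Kaplan-Meier is not always closer.** This stands. With half the event rate in lost women, the errors are about equal, and crude is slightly closer on the difference (9.6 against 10.5 points, true 10).
3. **The comparison is already planned with censoring.** This largely stands. What remains is which summary is reported as the retreatment rate.
4. **These are partly safety descriptions.** Protocol 3.4.3.d lists both outcomes under safety and additional treatment, and SAP 5.3 and 10.1 use all randomized women for safety. Observed events over that denominator are a fair description if labelled as such. SAP 7.3's sentence on imputation concerns secondary analyses, and retreatment is exploratory.
5. **The denominator wording foresees missing values.** It does, but no rule creates one, so the coding is under-specified and, followed literally, yields no missing values.

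A reader might infer that the retreatment comparison is invalid, or that the crude percentage must be discarded. The documents support neither: they give no observed loss or recording rates, and the ratio is unaffected by equal loss.

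**Conclusion.** The point holds as a minor one, with moderate confidence. Followed literally, SAP 9.2 gives a 12-month retreatment rate that is modestly too low whenever lost women's later events go unrecorded, and it conflicts with the SAP's own handling of the same women for time to failure. At 15% uniform, unrelated loss, the shortfall is about 2.3 and 1.5 points for a true 30% and 20%, and under 1 point in each arm for 10% and 5%. The resulting change in the difference is small against its confidence interval. The 30/20 rates and 15% loss are planning figures; the timing of loss, the recording shares, the unequal loss and the 10/5 rates are assumptions.

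A reader might also infer that the primary or secondary UDI tests are affected. The documents do not show this. SAP 9.3 has a model term for request for additional treatment, but nothing says that this 12-month rate indicator supplies it. For sling revision, the loss of a fraction of one event per arm is negligible.

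**What to change.** In SAP 9.2, for aim 5:

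- Report the 12-month Kaplan-Meier retreatment estimate by arm, with the difference and its confidence interval.
- Next to it, give the crude count labelled 'observed events only' and the number followed to 12 months in each arm.
- In the Kaplan-Meier estimate, count only events dated on or before the woman's censoring date. Events found later stay in the crude count.
- State that the estimate assumes non-informative censoring and, unlike the default model in SAP 9.1, is not adjusted for site and UUI stratum.
- Do not set event-free early losses to missing while keeping early 'Yes' cases.
- For sling revision, report the observed count by arm with the number followed. No further change is needed.

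The cost is a few sentences and a little extra output. The event dates, the censoring rule and the Kaplan-Meier analysis are already in the SAP. The price is the lost stratum adjustment and reliance on the censoring assumption, which is why the crude count should stay beside the estimate.

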9.3 Primary Analysis Methods

The mean change from baseline in UDI scores will be compared between groups at 1 year. As explained previously, participants will be permitted to seek additional treatment for SUI and/or OAB after 3 months following MUS. Because such treatment is expected to impact the participant's UDI score at 1 year, we will use an analysis method that accounts for the impact of additional treatment. Specifically, a general linear mixed model will be constructed to model change from baseline in UDI scores using scores recorded at time points up to 1 year following MUS. For participants who request additional treatment, only UDI measurements up to the time of additional treatment will be included in the model, and measurements taken between additional treatment and 1 year will be considered missing for the purpose of the primary analysis. The model will include fixed effects for treatment group, time, request for additional treatment, and interactions between those variables. It will also be adjusted for the design effects of stratification by center and by baseline urge IE group. Thus, the models will allow for different trajectories of change for women who are or are not randomized to BPTx and for those who do or do not request additional treatment. A statistical test based on the model will be conducted to assess whether mean changes from baseline in UDI scores at 1 year are significantly different between the two treatment groups, accounting for the percent of women in each group who request additional treatment. Sensitivity analysis will be conducted to test the robustness of test results to model specifications.

We will report whether change in total UDI score between baseline and one year is significantly different in the two groups. If the difference is statistically significant, the potential clinical significance of the difference will be discussed. We recognize that our sample size would allow us to find a difference between groups that is statistically significant yet smaller than published MIDs for total UDI score for women with MUI. However, published MIDs were calculated based on populations that may be somewhat different from the one targeted for enrollment in ESTEEM, and a secondary aim of ESTEEM is to explore whether the true MID in this population differs from previously published values.

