Published MIDs are important for estimating sample size and interpreting findings, however there are at least 3 different ways we can analyze the UDI scores:

- #1. Compare postoperative *mean UDI scores* between groups at 1 year
- #2. Compare *mean changes* (delta) in UDI scores from baseline to 1-year between groups (*preferred, see below*)
- #3. Dichotomize “success” and “failure” as women who achieved a 35 point improvement versus those who did not (also known as “responder analysis”)

We chose not to dichotomize our outcome for many reasons (option #3). Dichotomizing women as “success” or “failure” based on MID could simplify interpretation; however, using purely a responder analysis approach has limitations and some authors recommend avoiding this for primary analyses in trials.⁵² One disadvantage of responder analysis is reduced power and efficiency compared to analysis on the original scale, primarily due to the loss of information associated with lumping groups together. Particularly relevant to ESTEEM, some women could have *worse* scores compared to baseline and this information would be lost because they would be grouped with those who may have “slightly” improved, but

just not enough to be classified as a “success”. Also relevant to ESTEEM, if both groups worsened but one group “worsened less”, this information would also be lost using this approach.

Because the trial is randomized and we will be stratifying by UUI severity, we would expect the baseline UDI scores to be similar between groups. If the average baseline score is the same in the two groups, then comparing the mean change in UDI score between groups (option #2) is mathematically equivalent to comparing post-operative UDI scores at 1 year between groups (option #1). However, option #2 has some advantages in that (1) if baseline scores are not the same in the two groups, comparing the mean change in UDI score between groups at 12 months will account for that baseline difference, and (2) UDI scores typically have a distribution that is highly skewed, but differences from baseline should be close enough to being normally distributed that analysis methods that assume a normal distribution can be used.

3.4.1.a Rationale for using UDI as primary study outcome

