6.3 Final Sample Size

Using 200 per group as our base estimate and adjusting for 15% dropout post-operatively results in a total sample size of 472 randomized to treatment. Additionally, this sample size will provide approximately 90% power to detect a difference as small as 19 between treatment groups for the UDI-total score, and a difference as small as 16.5 points with 80% power.

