7.2 Adjustments for Covariates

Indicator variables for the study stratification factors of site and severity of baseline UUI (with a cut-off of ≥ 4 urge incontinence episodes on 3-day diary) will be included as covariates in most efficacy analyses performed for this study (details in section 9). Additionally, demographic and baseline characteristics for subjects and clinicians will be compared between study arms using analysis of covariance techniques for continuous measures, Mantel-Haenszel mean score test using standardized midrank scores for ordinal measures, and Cochran Mantel-Haenszel chi-square tests for general association for categorical measures. If sample sizes allow, these analyses will control for the study stratification factors. If these analyses suggest that substantial differences exist among arms, the use as covariates of these parameters on which the arms differ will be explored in secondary exploratory analyses of the efficacy data.

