clinical site will be included as random intercepts to account for correlation between outcomes of patients treated by the same clinical site. Consistent with the description of the primary analysis in the protocol, analyses of primary and secondary outcomes will also include independent variables for time and request for additional treatment. If differences between treatment groups are to be assessed at multiple time points (for example, 6 and 12 months), then longitudinal modeling will be used and the interaction between time and treatment groups will be included. Unless otherwise noted, all analyses of continuous efficacy variables (e.g., QOL scales) will be performed using general linear mixed models. Variables with distributions substantially different from normal will be transformed prior to analysis. Models will be adjusted for clinical site and UUI severity group. If there are not enough patients per clinical site to include the variables in the models as fixed effects, clinical site will be included as a random intercept to account for correlation between outcomes of patients treated by the same clinical site. If differences between treatment groups are to be assessed at multiple time points (for example, 6 and 12 months), then longitudinal modeling will be used and the interaction between time and treatment groups will be included. Under the assumption that any missing outcome data will be missing at random (thus, missing UDI scores at 12 months may be related to both 3 and 6-month outcomes and covariates), this model will produce more accurate estimates in the presence of missing data than one that models only outcomes at 12 months. For the primary outcome and for secondary outcomes, models will include 2- and 3-way interactions between treatment assignments, time, and request for additional treatment.

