9.4 Secondary Analysis Methods

The mean change from baseline in UDI-irritative and UDI-stress scores at 1 year will be compared between groups using the same analysis methods described for the primary analysis. If the difference is statistically significant, the potential clinical significance of the difference will be discussed. Additional analyses will be conducted to determine whether the MIDs in this MUI population differ from previously published MIDs.

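### The UDI models analyze change without baseline UDI as a covariate: the test is valid, but it gives up precision and over-corrects a chance baseline imbalance if the baseline-to-12-month slope is below 1

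*SAP*

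**What the plan says.** SAP 9.3 (and Protocol 6.2.1, in the same terms) fits a general linear mixed model to change from baseline in UDI. Its fixed effects are treatment, time, request for additional treatment and their interactions. On further covariates it says: "It will also be adjusted for the design effects of stratification by center and by baseline urge IE group". SAP 9.2 defines the outcome as the follow-up score minus the baseline score, so baseline enters only by subtraction. SAP 9.1 repeats the rule for continuous outcomes: "Models will be adjusted for clinical site and UUI severity group". Under SAP 9.4 the irritative and stress subscales are "compared between groups using the same analysis methods described for the primary analysis".

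Protocol 3.4.1 gives two reasons for preferring change scores. One is that, if the arms differ at baseline, "comparing the mean change in UDI score between groups at 12 months will account for that baseline difference". The other is that UDI scores are skewed while changes should be closer to normal.

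Three other provisions come near the point:

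- SAP 7.2: if the arms are seen to differ, "the use as covariates of these parameters on which the arms differ will be explored in secondary exploratory analyses of the efficacy data".
- SAP 9.3: "Sensitivity analysis will be conducted to test the robustness of test results to model specifications", with no specification named.
- SAP 16.2 imputes using baseline values, but then "Each imputed dataset will be fit using the models described in Section 9.3".

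**The concern.** Subtracting baseline fixes its coefficient at 1. If the true slope of the 12-month score on baseline is lower, the change score carries avoidable baseline noise, and all three UDI comparisons are less precise than the data allow. The first reason in Protocol 3.4.1 is then also wrong. The comparison does not simply account for a baseline difference; it over-corrects it by (1 − slope) per point and credits the arm that started worse. SAP 9.3 itself anticipates a result that is significant yet below published MIDs, and a few points of over-correction matter most there.

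None of the three nearby provisions puts baseline UDI into the primary model. By contrast, the cost-effectiveness analysis in Protocol 6.2.3(h) adjusts QALYs for baseline utility precisely because of possible imbalance.

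**Working it through.** **The plan's own figure.** SAP 6.3 claims "approximately 90% power to detect a difference as small as 19 between treatment groups for the UDI-total score". With SD 50.4 (SAP 6.1), two-sided 0.05 and 200 per arm, the plain formula gives (1.960 + 1.282) × 50.4 × √(2/200) = 16.3 points. Removing the average 25% who seek additional treatment (30% and 20%, SAP 6) leaves 150 per arm and gives 18.9 points, with power 0.904 at 19 points and 0.809 at 16.5. The stated figures are therefore reproduced.

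**Inputs.**

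- Baseline SD s0 = 49, the urge-predominant population in Protocol 3.4.1.
- SD 50.4, taken as the SD of change. The SAP does not say so explicitly.
- 12-month SD s1 = 30 to 49. This is an assumption; the documents give no value for UDI-total.

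**Closed form, single visit.**

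- ρ = (s0² + s1² − 50.4²)/(2·s0·s1)
- slope b = ρ·s1/s0
- adjusted variance Va = s1²(1 − ρ²)
- gap from the change-score variance = s0²(1 − b)²
- allowing for an urge IE stratum that correlates 0.4 with baseline UDI (assumed): ratio = Va/[Va + (1 − b)²·s0²·(1 − 0.4²)]
- one-SE chance baseline difference at 200 per arm = 49 × √(2/200) = 4.9 points; over-correction = 4.9 × (1 − b)

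| s1 | ρ | slope | variance ratio | ratio with stratum | over-correction |
|---|---|---|---|---|---|
| 30 | 0.26 | 0.16 | 0.33 | 0.37 | 4.1 |
| 40 | 0.37 | 0.30 | 0.54 | 0.59 | 3.4 |
| 49 | 0.47 | 0.47 | 0.74 | 0.77 | 2.6 |

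**Simulation closer to the planned model.** There were 1,500 replicates per scenario, with 236 women per arm, visits at 3, 6 and 12 months, and a time × arm × request model whose 12-month contrast was weighted by observed request rates. Additional-treatment rates were 30% and 20% and dropout was 15%. Further assumptions: requesters 30 points worse with only pre-treatment scores kept, correlation 0.6 between follow-up visits, a median-split stratum correlated 0.4 with baseline, and variances treated as known.

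| s1 | SE, planned | SE, adjusted | variance ratio | 19 points becomes | shift per point of imbalance, planned | adjusted |
|---|---|---|---|---|---|---|
| 30 | 4.82 | 3.36 | 0.49 | 13.2 | −0.81 | 0.02 |
| 40 | 5.36 | 4.47 | 0.70 | 15.8 | −0.70 | 0.00 |
| 49 | 5.78 | 5.33 | 0.85 | 17.5 | −0.53 | 0.00 |

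The fifth column is 19 × SE adjusted/SE planned. A second simulation with the same features gave variance ratios of 0.48, 0.66 and 0.80.

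**Cross-check on the 19 points.** Hold the excess over the plain formula fixed (19² − 16.3² ≈ 94) and shrink only the rest by the closed-form ratios with the stratum. This gives 13.9, 15.8 and 17.3 points.

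**Validity.** In 5,000 simulated single-visit trials per setting with no true effect, the change-score test rejected in 5.4% (SDs 49/49, ρ 0.47) and 4.5% (SDs 25.4/15.1, ρ 0.284). With baseline adjustment the figures were 5.1% and 4.6%.

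**Subscales.** With baseline SDs 22 (irritative) and 19 (stress) from Protocol 3.4.1, planning SDs 25.6 and 21.5 read as change SDs, and equal SDs at baseline and 12 months, ρ = 1 − SD²/(2·s0²) = 0.32 and 0.36. The variance ratio (1 + ρ)/2 is 0.66 and 0.68. The TOMUS irritative SDs in Protocol 2.5 (25.4 before, 15.1 at 12 months) cap the slope at 15.1/25.4 = 0.59 whatever the correlation, with ratios of 0.26 to 0.35 for correlations of 0 to 0.7. Protocol 4.1.2 targets more severe urge symptoms than TOMUS, so this is a pointer only.

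**The case against.** The strongest reply is that this is a deliberate, explained efficiency choice in a trial that meets its stated power: UDI-total has 90% power at 19 points against a 35-point planning MID. That is right, and it is why the point does not concern validity. It does not argue against a more precise estimate from data already collected.

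The size is open to dispute, in part fairly:

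- Multiplying the simulated change-model SEs by 3.24 gives 15.6, 17.4 and 18.7 points. Only the last, at 12-month SD 49, matches the plan's 19, so a gain of about 1.5 points is the better-supported end and 13.2 is the favorable extreme.
- Protocol 3.4.1 also gives a baseline SD of 40. With 12-month SD 49 the single-visit ratio is then 0.81, milder than 0.74 but still a loss.
- Allowing for the stratum, the one-SE imbalance is 4.9 × √0.84 = 4.5 points and the over-correction 2.4 to 3.8.
- Averaged over randomizations, over-correction and lost precision are the same quantity, already inside the confidence interval. Over-correction is a separate matter only when one observed imbalance has to be interpreted.

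On skewness, keeping change as the response does not wholly dispose of the worry, because the adjusted residuals are those of the 12-month score given baseline. They need checking, but that is no reason to omit the covariate. Finally, validity here refers only to the omission of baseline. Conditioning on request for additional treatment, a post-randomization variable, was not tested.

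**Conclusion.** The concern holds. Baseline UDI is absent from the primary model and from both secondary models, and no other provision supplies it. Leaving it out does not bias the comparison over randomization or inflate type I error. It does give up precision unless the slope is exactly 1, and the claim in Protocol 3.4.1 that change accounts for a baseline difference is exact only at that slope.

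Under the assumptions above, the adjusted variance is 0.49 to 0.85 of the planned variance for UDI-total. The true figure depends on a 12-month SD and correlation that the documents do not give. The omission itself and its direction are certain; the size is approximate. The change should be made, but the planned analysis is not unsound without it.

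**What to change.** In SAP 9.3 add baseline UDI-total and its interaction with visit as covariates. In SAP 9.4 add the matching baseline subscale in the same way. Keep change as the response, so the contrast remains the difference in mean change at 12 months. Make the same edit in Protocol 6.2.1 and 6.2.2, and correct the first reason for change scores in Protocol 3.4.1.

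The cost is two model terms per outcome and no new data. Check the residuals for skewness and specify robust standard errors as a fallback.

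Timing matters. SAP 13 reports the switch to Kaplan-Meier methods in the past tense, so this version may follow sight of some data. If treatment groups have been unmasked, keep the planned model as primary and name the baseline-adjusted model as a labelled sensitivity analysis under the existing provision in SAP 9.3.
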